ClinicalTrials.gov Protocol Registration and Results System (PRS) Receipt
Release Date: May 29, 2024

ClinicalTrials.gov ID: [Not yet assigned]

Study Identification

Unique Protocol ID: IIT2023015

Brief Title: Comparison of Short-term and Long-term Outcomes of Robotic and Laparoscopic Right Colon Cancer: a 10-year Single-center Large-sample Retrospective Study

Official Title: the Ethics Committee of the First Affiliated Hospital of Nanchang University

Secondary IDs:

Study Status

Record Verification: May 2024

Overall Status: Completed

Study Start: December 1, 2014 [Actual]

Primary Completion: March 31, 2024 [Actual]

Study Completion: April 30, 2024 [Actual]

Sponsor/Collaborators

Sponsor: [name]

Responsible Party: Sponsor-Investigator

Investigator: [name] [[name]]

Official Title: the First Affiliated Hospital of Nanchang University

Affiliation: Nanchang University

Collaborators:

Oversight

U.S. FDA-regulated Drug: No

U.S. FDA-regulated Device: No

U.S. FDA IND/IDE: No

Human Subjects Review: Board Status: Exempt

Data Monitoring:

Study Description

Brief Summary: The goal of this observational study is to evaluate the short-term outcomes and long-term outcomes of robot-assisted right colon group for cancer compared

to laparoscopic-assisted right colon group. This is a large sample study based on ten years of clinical data. The main question it aims to answer is: What are the advantages of da Vinci robot right hemicolectomy compared to laparoscopic right hemicolectomy, and is there a difference in long-term efficacy between the two methods.

Detailed Description:

Conditions

Conditions: Robotic, Laparoscopic, Colon Cancer, Short-term Outcomes, Long-term Outcomes

Keywords:

Study Design

Study Type: Observational

Observational Study Model: Cohort

Time Perspective: Retrospective

Biospecimen Retention:

Biospecimen Description:

Enrollment: 1879 [Actual]

Number of Groups/Cohorts: 2

Groups and Interventions

| Groups/Cohorts | Interventions |
|---|---|
| robot-assisted right colon group Robot assisted radical surgery for right colon cancer | Device: Da Vinci Robot Surgical System Performing surgery on right colon cancer patients using the da Vinci robotic surgical system or laparoscopic surgical system Other Names: 
• Laparoscopic surgical system |

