| laparoscopic-assisted right colon group Laparoscopic assisted radical surgery for right colon cancer | Device: Da Vinci Robot Surgical System Performing surgery on right colon cancer patients using the da Vinci robotic surgical system or laparoscopic surgical system Other Names: 
• Laparoscopic surgical system |

Outcome Measures

Primary Outcome Measure:

1. overall survival
[Time Frame: months]
2. disease-free survival

[Time Frame: months]

Secondary Outcome Measure:

3. the rate of postoperative complications

[Time Frame: rates]

4. operative time

[Time Frame: minute]

5. estimation of blood loss

[Time Frame: ml]

6. number of retrieved lymph nodes

[Time Frame: Number]

7. days after postoperative hospital stay

[Time Frame: day]

8. time to first exhaust

[Time Frame: hours]

9. time to liquid diet

[Time Frame: hours]

10. the rate of intracorporeal anastomosis

[Time Frame: rates]

Eligibility

Study Population: The consecutive cases of robotic-assisted or laparoscopic-assisted right colectomy between December 2014 and March 2024. All cases derived from the First Affiliated Hospital of Nanchang University.

Sampling Method: Non-Probability Sample

Minimum Age: 18 Years

Maximum Age: 85 Years

Sex: All

Gender Based:

Accepts Healthy Volunteers: No

Criteria: Inclusion Criteria:1) age: 18-85 years; 2) no distant metastasis; 3) preoperative colonoscopy showing that the tumor was located in the ileocecal region, ascending colon, hepatic flexure, or transverse colon with pathology showing malignancy; 4) signed informed consent.

-

Exclusion Criteria:1) multiple primary colorectal cancer; 2) recurrent right colon cancer; 3) preoperative neoadjuvant chemotherapy; 4) emergency surgery for intestinal obstruction, bleeding or perforation; 5) incomplete data and missing follow-up data.

-

Contacts/Locations

Central Contact Person: [name], doctor

Email: [contact]

Central Contact Backup: [name], doctor

Study Officials:

Locations:

IPDSharing

Plan to Share IPD: Undecided

Access to the database can be obtained from the corresponding author on reasonable request.

References

Citations:

Links:

Available IPD/Information:

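### Exclusion criterion 5 makes cohort entry depend on information that arises only after surgery; if it removes patients with partial follow-up, OS reads equal to or lower than with censoring and DFS is distorted in an uncertain direction

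*Protocol*

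**What the plan says.** The Protocol's Eligibility section gives the source population as "The consecutive cases of robotic-assisted or laparoscopic-assisted right colectomy between December 2014 and March 2024". Exclusion criterion 5 then removes patients for "incomplete data and missing follow-up data". Neither half of that phrase is defined, and nothing says whether a patient with some follow-up is kept and censored.

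Under Outcome Measures, the two primary outcomes are "overall survival" and "disease-free survival", both in months. Eight secondary outcomes follow, all perioperative, including "the rate of postoperative complications". The Brief Summary asks, among other things, "is there a difference in long-term efficacy between the two methods".

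Study Design gives an actual enrolment of 1879, without saying whether this is before or after criterion 5 was applied. No number excluded, loss rate or split by surgical group is given.

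**The concern.** The other eligibility criteria can be settled by the time of surgery. Criterion 5 cannot: whether follow-up is complete is known only later, and may depend on how the patient fared. Survival analysis handles a patient who is lost by counting the time observed and then censoring. An exclusion rule discards that time, while a patient who died before being lost is kept.

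At stake are the OS and DFS estimates in each group and, if loss or calendar time of surgery differs between robotic and laparoscopic patients, the comparison itself. The short-term outcomes are also affected, because a patient removed for missing follow-up takes a recorded operative time, blood loss and complication status out of the analysis.

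This is not detail that a protocol commonly leaves to an SAP. The rule is an eligibility criterion, and an SAP cannot censor patients whom that criterion has kept out.

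**Working it through.** The Protocol states no survival, loss or event figure, so there is nothing to reproduce. **All rates below are assumptions.** From the Protocol come the accrual window (December 2014 to March 2024 = 1 + 9×12 + 3 = 112 months) and the count of 1879. Entry is taken as uniform over the window unless stated, with follow-up cut at its end. The true hazard ratio is 1.00.

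**1. Direction for OS (partial follow-up removed).** The Kaplan-Meier estimate is the product of factors 1 − d/n. A patient lost alive contributes to n up to the time of loss and never to d. Removing that patient leaves every d unchanged and lowers n at earlier death times, so each factor falls or stays equal. In 500 simulated samples of 1879 (5-year OS 80%, 10% loss), checked at 12, 36, 60 and 100 months, the reduced estimate was never above the censored one.

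**2. Size for OS.** Let λ be the death hazard and μ the loss hazard, both constant and independent, with G(u) = 1 − u/112 and g = 1/112 for administrative censoring. Among those kept, the at-risk function is R(t) = ∫ from t to 112 of exp(−(λ+μ)u)[λG(u) + g]du, and the apparent hazard is h(t) = λ exp(−(λ+μ)t)G(t)/R(t).
- OS 75%, 20% lost by 5 years: λ = −ln(0.75)/60 = 0.004795 and μ = −ln(0.80)/60 = 0.003719. exp(−∫h over 0 to 60) = 0.721.
- OS 85%, same loss: 0.830.
- Fraction removed, 1 − R(0), at OS 75%: 3.9%, 15.5% and 23.2% for 5%, 20% and 30% loss. If 1879 is the count after exclusion, 1879·p/(1 − p) gives about 77, 345 and 566 patients.

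**3. Hazard ratio for OS.** Solving the Cox score equation for two equal-sized groups with the same true survival:

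| Situation | OS HR, 5-year OS 75% | OS HR, 5-year OS 85% |
|---|---|---|
| Loss 20% v 20%, same dates | 1.00 | 1.00 |
| Loss 5% v 15% | 1.06 | 1.07 |
| Loss 5% v 20% | 1.10 | 1.11 |
| Loss 10% v 30% | 1.15 | 1.16 |
| Loss 20% in both, uniform v late surgery dates | 1.04 | 1.05 |
| Loss 20% in both, early v late surgery dates | 1.07 | 1.08 |

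The HR is for the higher-loss group, or the group operated on earlier. Censoring gives 1.00 throughout.

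**4. DFS.** Illness-death model: 5-year DFS 70%, 80% of first events are recurrences, 20% loss by 5 years, and a patient is dropped if lost before death and before the cut. Dropping such a patient after recurrence deletes a DFS event, which works against the deleted event-free time.
- Loss unrelated to recurrence: DFS reads 67.6%, 68.1% and 68.6% for a median survival after recurrence of 12, 24 and 60 months. Censoring reads 70.0%.
- Loss more frequent after recurrence, dropped v censored: 60-month median, 2 times, 70.3% v 70.0%; 24-month, 3 times, 70.3% v 70.0%; 12-month, 5 times, 70.5% v 70.0%; 60-month, 5 times, 74.3% v 70.0%.

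The sign for DFS is therefore not fixed.

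**5. Only patients with no follow-up removed.** With discharge at an assumed 0.33 months and p = 30% removed, the change in 5-year OS is 0.75 × (1 − exp(−λ × 0.33 × p/(1 − p))) = 0.0005, or 0.05 points. The HR moves by about 0.002. For short-term outcomes the standard error grows by (1 − p)^−0.5: 2.6%, 5.4% and 11.8% at 5%, 10% and 20% removed. Bias needs related loss: with 10% removed and complications in 30% of them v 20% of those kept, the true rate is 0.1×30 + 0.9×20 = 21%, read as 20%.

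**6. Incomplete data.** Read as any of the eight secondary outcomes missing, with a fraction m missing for each independently, 1 − (1 − m)^8 = 7.7%, 14.9% and 33.7% of patients go at m = 1%, 2% and 5%. If the gaps fall in the same patients, only 1%, 2% and 5% go.

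**The case against.** The strongest objection is that the harm to the primary outcomes rests on one reading. The phrase can mean that no follow-up exists at all, and taken literally the word joining its two halves could require both defects, which would remove fewer patients. Nothing in the Protocol says that patients with partial follow-up were dropped. This stands, and it makes the OS and DFS conclusion conditional. It does not make the rule sound: even the narrow reading discards recorded perioperative results, and the wording lets the broad one be applied.

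Three stronger inferences are tempting, and the Protocol does not support them.
- A reader might infer that DFS, like OS, must read too low. Step 4 shows that it need not.
- A reader might infer that the robotic v laparoscopic comparison is biased. That needs loss rates or surgery dates that differ by group, and the Protocol reports neither. With both equal the HR stays at 1.00.
- A reader might infer that calling the cases consecutive contradicts the exclusions. The word describes the source population, to which five exclusions are then applied. What sets criterion 5 apart is that it depends on post-surgical information and is undefined.

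It can also be said that censoring is not always nearer the truth. If lost patients then die at three times the rate (20% loss, OS otherwise 75%), true 5-year OS is exp(−60(λ+μ)) + ∫ from 0 to 60 of μ exp(−(λ+μ)u) exp(−3λ(60−u))du = 71.3%. Censoring reads 75.0% and dropping reads 72.1%. This stands, and is a reason to show both results. It is no reason to keep the exclusion, because the dropped estimate is closer there only by offsetting errors.

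**Conclusion.** The point holds in conditional form and should be fixed. Criterion 5 selects patients on information arising after surgery. If it covers partial follow-up, OS is equal to or below the censored estimate with certainty, by about 2 to 3 points at 5 years under an assumed independent 20% loss. Below means relative to censoring; it also means below the truth only if loss is unrelated to prognosis. DFS is distorted unless opposing effects cancel, and its direction depends on whether patients are lost more often after recurrence. A spurious OS hazard ratio of about 1.10 would need something like 5% v 20% loss between groups. If the criterion covers only patients with no follow-up, the primary outcomes are essentially untouched, and the cost is precision in the short-term outcomes, with bias only if loss is related to them.

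Which reading applied, how many patients were removed and from which group cannot be told from the Protocol, so neither the size nor the effect on the comparison in this study is established.

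**What to change.** Remove loss to follow-up as an exclusion, and do not exclude patients for missing outcome data. One workable limit for the other half of criterion 5 is to apply it only where eligibility or surgical group cannot be established. Keep all otherwise eligible patients, censor OS and DFS at last known contact (at discharge if there is none later), and analyse each short-term outcome in all patients who have it recorded.

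Report by group how many patients criterion 5 removed as applied, and whether 1879 is before or after that step. Show the analysis with the exclusion as a sensitivity analysis beside the censored one.

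Cost: the study is recorded as completed, so the excluded chart records must be re-extracted, last-contact dates added and the analyses rerun. No new patients or procedures are needed.
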